3.2.3. Duration of the investigation

Accrual of study subjects will occur over approximately 5 years with all subjects to be followed at 1 month, 6 month, and 12 month intervals post-procedure followed by annual follow-up through 5 years post implant. Per standard of care, the patients will undergo lifelong follow-up after they have completed the study.

3.3 Protocol

This study will be conducted with non-surgical or very high-risk patients who are considered suitable candidates for endoluminal repair. Adult male and female patients who fulfill the inclusion/exclusion criteria listed below are eligible for enrollment.

3.3.1. Inclusion Criteria

In order to qualify for this physician-sponsored Investigational Device Exemption, the patients would have to meet the entire entry criteria listed below, sign a consent approved by the FDA and IRB, and agrees to follow-up according to the study protocol.

1. Patient must have a type A thoracic aortic dissection, retrograde type A thoracic aortic dissection of the ascending thoracic aorta affecting the area between the Sinus of Valsalva and the innominate artery orifice (with no involvement of the aortic valve), and be considered a candidate for endovascular repair;
 - 1.1. The proximal landing zone will allow placement of the statement of the stent graft as to not inhibit valvular function, occlude a coronary ostium or proximal bypass graft;
 - 1.2. Distal landing zone must allow for continued perfusion of critical cerebral vessels;

- 1.3. Ascending aorta between 28-44 mm in diameter;
- 1.4. The patient must be high-risk surgical candidate according to the following established criteria:
ASA score of IV.

3.3.2. Exclusion Criteria

The following patients are excluded from this study:

1. Pregnant or pediatric patients (younger than 21 years of age);
2. Patients who have a condition that threatens to infect the stent graft/aortic valve prosthesis;
3. Patients with allergies to the stent graft material;
4. Patients or their legally authorized representative (LAR) who does not sign the informed consent.
5. Patients with expected survival less than one year due to a condition other than the ascending aortic dissection.

3.3.3. Study Design

This early feasibility study is a prospective evaluation of patients receiving the device to determine the proportion in whom successful implantation is achieved, as indicated by exclusion of the thoracic lesion and graft patency at implant, time of discharge, and 1, 6, and 12 months, and annual visits through 5 years following implantation, and to determine the proportion of patients who die or experience adverse events during and after the implantation. Furthermore, the percentage of patients in whom technical and clinical success is achieved, will be determined. Additional endpoints include length of stay in intensive care unit following the procedure, and total length of hospital stay.

Twenty patients will be enrolled in this feasibility study. The enrollment will be performed in five-patient increments, and the results of each five-patient group will be analyzed and reported prior to enrolling further patients. This modus operandi serves as risk mitigating strategy.

3.3.4. Study Procedures

3.3.4.1 Patient Screening and Enrollment

Investigators will assess potential subjects diagnosed with Type A thoracic aortic dissection, retrograde Type A thoracic aortic dissection of the ascending thoracic aorta for their suitability for enrollment in the clinical study. If the patient appears to meet the eligibility criteria, the investigator will discuss the study with the patient and provide information relating to the potential risks and benefits, and required follow-up procedures per the informed consent process. After the patient has voluntarily signed and dated the informed consent document, the patient will be considered a study candidate. If a patient does not sign the informed consent document, then no further procedures for the clinical study will occur. Subjects who were considered for the study but do not qualify for enrollment will be documented as ineligible on the Subject Screening Log. Subjects enrolled, but with no device implant will be followed through the one-month follow-up only.

Those subjects who sign and date the informed consent document, or who have their Legally Authorized Representative sign and date the informed consent document, and meet all of the study eligibility criteria will be eligible for enrollment into the clinical study. The subject will be considered enrolled at the time the Medtronic Thoracic Stent Graft System is introduced into the arterial access vessels.

Documentation of the following will be obtained prior to the implant procedure:

- Informed consent
- Demographic data
- Medical history
- Vital signs [heart rate, blood pressure, respiratory status, pulse evaluation
(Left and right Radial, Dorsalis, and/or Tibial artery)]
- Pregnancy test (females of child bearing potential)
- Clinical laboratory tests: serum creatinine
- CT of the Chest/Abdomen/Pelvis with and without contrast; MRA, may be used at the investigator's discretion.
- Echocardiogram

All subjects will undergo a neurological examination when possible depending upon the urgency of the procedure and patient availability.

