In some subjects there may be difficulty inserting and implanting the Medtronic Thoracic Stent Graft System during the procedure. If it is not possible to complete implantation of the device, or if peri- or post-operative complications arise that place the subject at risk, the Clinical Investigator/Sponsor may elect to convert the patient to open surgery. Alternatively, the Clinical Investigator/Sponsor may elect not to repair the dissection/hematoma, and to manage the patient with observation only. This is especially true for patients who are deemed not operative candidates. In such cases, the reason for conversion must be recorded on the Procedure CRF.

Also, as noted previously, subjects who convert to surgery or who are managed by observation will be followed in an identical manner as the other subjects. A Post- Operative Assessment CRF will be completed at 1, 6, and 12 months after the attempted implantation.

Death

Autopsies will be requested for subjects who expire following implantation of a Medtronic Thoracic Stent Graft System. If the patient or the family consents to a post- mortem exam, the device will be explanted whenever possible for examination and histological analysis. The Clinical Investigator/Sponsor will request that the explanted device be sent to the designated facility for examination and histological analysis. The Clinical Investigator/Sponsor will determine whether or not the device (or procedure) caused or contributed to the subject's death.

Other Adverse Events

The health risks associated with use of the Medtronic Thoracic Stent Graft System may be less than for conventional surgical treatment. However, as with any medical procedure, there are some risks. There is the potential for discomfort or complications resulting from the procedure and the implanted stent graft. It is hypothesized that the rate of serious adverse events in stent-graft patients will be less as compared to an expected serious adverse event rate for surgical patients.

The following is a non-exhaustive list of potential serious complications that may occur during or following implantation of the Medtronic Thoracic Stent Graft System:

- embolization that may lead to stroke, amputation, intestinal ischemia, multiple organ failure, or death;
- renal insufficiency or failure, that may necessitate dialysis;
- unsuccessful repair or early endoleak, possibly leading to rupture of the aorta and death;

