3.3.4.9. Withdrawal and Lost to follow-up

Patients may be withdrawn from the study for a number of reasons. The following is a summary of the possible reasons for withdrawal:

- Subjects may voluntarily withdraw from the study. The reason for withdrawal must be documented on the Termination CRF
- After the implant procedure, some subjects may not return for follow-up visits. A minimum of three (3) attempts to contact such patients must be made. All attempts are to be documented on the Termination CRF.

In some cases, an implant procedure will be initiated (i.e., an attempt to pass or deploy the device) but is aborted prior to device deployment. Such patients maintain their enrollment status (since this is an intent-to-treat study), but need not be followed. On the other hand, if a patient is initially screened and enrolled, but no procedure is ever initiated, the patient is cancelled and his/her enrollment position is made available to another patient.

Patients who are enrolled in the study group and are converted to surgery due to peri- or post-implantation complications will be followed for a minimum of 12 months after the conversion to open repair. Conversion to surgery is documented on the Procedure CRF.

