3.3.5.1 Description of Endpoints

Primary endpoints will be early (at 30-days) and late death (at one-, two- and five-years), re-interventions, and surgical conversion (early or late), as well as any post-procedural stroke (early or late), ischemic or hemorrhagic events causing motoric, language or cognitive compromise.

Secondary endpoints will include access vessel complications (including dissection, thrombosis, embolization), myocardial infarction, renal failure, sepsis, pulmonary failure, blood loss over 1000cc, stent graft migration, endoleaks, technical observation (including twisting, kinking, or fracture), loss of stent graft patency (occlusion), aortic valve function (AI>2+), and any malperfusion to aortic branch-vessels (diagnosed with CTA or clinical diagnosis).

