3.3.5.3. Analysis of Endpoints

Data Analysis Sets

The primary endpoint analysis set will include all enrolled subjects who had at least one study stent graft implanted.

The Intent-to-Treat (ITT) analysis set will include all enrolled subjects who had an infra-arterial access procedure with intent to receive the study device. The primary endpoint will be reported for this analysis set as well.

Analysis of the Primary Endpoint

The primary endpoint will be analyzed using the exact binomial test method. The null hypothesis will be rejected if the upper limit of the one-sided 95% confidence interval on the 30 days mortality rate is less than 25%. The one-sided upper 95% confidence interval on the 30 days mortality rate will be calculated using the exact binomial test method.

The remainder of the primary endpoint will be presented and analyzed descriptively by reporting, for categorical variables, the number of known values and the percentage in each category, and for continuous variables, the number of known values, the mean, standard deviation (SD), median and the minimum and maximum number of subjects.

Analysis of the Secondary Observations

All secondary endpoints will be presented descriptively by reporting, for categorical variables the number of known values and the percentage in each category, and for continuous variables the number of known values, mean, standard deviation (SD), median, minimum and maximum of subjects meeting the endpoint.

Analysis of Baseline Variables

Baseline variables will be presented descriptively as described in the section above.

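### Follow-up rules for aborted, observed and converted subjects disagree, so the ITT primary endpoint is not assured

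*Combined protocol and SAP*

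**What the plan says.** A subject counts as enrolled once the device is introduced into the arterial access vessels (Section 3.3.4.1). Someone whose implant is then abandoned is therefore enrolled. The plan says the following about subjects who are not implanted, or who are converted:

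- Section 3.3.4.1: "Subjects enrolled, but with no device implant will be followed through the one-month follow-up only".
- Section 3.3.4.9, on procedures aborted before deployment: "Such patients maintain their enrollment status (since this is an intent-to-treat study), but need not be followed".
- Section 3.3.4.8, under Conversion to Surgery: "subjects who convert to surgery or who are managed by observation will be followed in an identical manner as the other subjects". The next sentence schedules the Post-Operative Assessment form for 1, 6 and 12 months after the attempt.
- Section 3.3.4.9, on subjects converted because of complications during or after implantation: they "will be followed for a minimum of 12 months after the conversion to open repair".

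The endpoint text in Section 3.3.5.1 reads: "Primary endpoints will be early (at 30-days) and late death (at one-, two- and five-years), re-interventions, and surgical conversion (early or late"), with stroke added. Section 3.3.5.3 makes implanted subjects the primary endpoint analysis set. It defines an ITT set of enrolled subjects who had arterial access with intent to receive the device, and says of it: "The primary endpoint will be reported for this analysis set as well". The only tested component is 30-day death: the null is rejected if the "upper limit of the one-sided 95% confidence interval on the 30 days mortality rate is less than 25" per cent.

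**The concern.** The ITT set exists to include failed procedures, and those are the subjects for whom the plan reduces or waives data collection. Section 3.3.4.9 invokes intent-to-treat and, in the same sentence, gives up the outcome data that an ITT report needs.

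What gets collected would depend on which section the site happens to follow. No rule for missing outcomes is given. The descriptive components are reported on the number of known values, so an unfollowed subject could drop out of the denominator unnoticed. In a study of this size ("Twenty patients will be enrolled in this feasibility study"), one or two such subjects can change the 30-day ITT conclusion, and outcomes not collected at the time may not be recoverable later.

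**Working it through.** **1. The rules side by side.** The general schedule is 1, 6 and 12 months, then annually to 5 years (Section 3.2.3).

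| Rule | Applies to | 30 days | 1 year | 2 and 5 years |
|---|---|---|---|---|
| 3.3.4.1, one month | enrolled, no implant | broadly | no | no |
| 3.3.4.9, no follow-up | aborted before deployment | no | no | no |
| 3.3.4.8, same as others | converted or observed | yes | yes | yes |
| 3.3.4.8, forms at 1, 6, 12 months | converted or observed | yes | yes | no |
| 3.3.4.9, 12-month minimum | converted | yes | yes | not assured |

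A subject whose implant is aborted and who is then only observed falls under Sections 3.3.4.1, 3.3.4.8 and 3.3.4.9 at once, and they give different answers. Only the same-as-others reading of Section 3.3.4.8 supplies 2- and 5-year status.

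**2. The implanted set is touched as well.** A subject implanted and later converted belongs to the implanted primary set. The 12-month minimum and the 1-, 6- and 12-month forms leave that subject's 2- and 5-year status unassured. The final assessment in Section 3.3.4.10 is for implanted subjects who choose to leave the study early, so it does not cover non-implanted subjects.

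**3. The one-month window.** The visit may fall 14 days either side (Section 3.3.4.4). Taking one month as 30 days, 30 − 14 = day 16. A subject followed only to that visit can have unknown status at day 30.

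**4. Size for the 30-day ITT report.** The plan gives no power, expected rate or derivation of n = 20, so there is no figure of its own to reproduce. Inputs: n = 20 (Section 3.3.3), 25% threshold and exact one-sided 95% upper limit (Section 3.3.5.3). The number of unknown subjects, m, is an assumption.

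For x deaths in n, the upper limit U(x, n) is the 95th percentile of Beta(x + 1, n − x):

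- U(0, 20) = 13.9%, pass
- U(1, 20) = 21.6%, pass
- U(2, 20) = 28.3%, fail

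With complete data, success therefore means at most one death. With d known deaths, the best case counts every unknown as alive, U(d, 20), and the worst case counts every unknown as dead, U(d + m, 20):

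| Known deaths d | Unknown m | Best | Worst | Conclusion |
|---|---|---|---|---|
| 0 | 1 | 13.9% | 21.6% | pass either way |
| 0 | 2 | 13.9% | 28.3% | undetermined |
| 1 | 1 | 21.6% | 28.3% | undetermined |

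With two known deaths the ITT criterion already fails. Each unknown subject widens the range of the mortality proportion by 1/20 = 5 percentage points, at 30 days and equally at 1, 2 and 5 years.

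**5. If unknowns are dropped instead.** With one known death, U(1, 19) = 22.6%, U(1, 18) = 23.8% and U(1, 17) = 25.01%. One or two dropped subjects give a pass and three give a fail, whatever happened to them.

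**The case against.** A reader might infer that the ITT endpoint cannot be computed at all. The documents do not support that. Every rule except the waiver for aborted cases reaches about 30 days, one-year death is covered for converted subjects under Sections 3.3.4.8 and 3.3.4.9, and one reading of Section 3.3.4.8 gives the full 5 years. If every subject is implanted and none converted, the problem does not arise.

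A reader might also treat the four statements as mutually contradictory. They are not: the 12-month minimum fits the 1-, 6- and 12-month forms.

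It is tempting to say that one lost subject turns a fail into a pass. With 19 implanted and one death, 1/19 is the implanted set's result by definition, and better follow-up of the non-implanted subject would not change it. Only the additional ITT report moves, and one unknown decides it only when exactly one death is known.

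The conversion rates cited in Section 2.1.1 (3.4% and 2 of 22) would give a 50% to 85% chance of at least one event in 20: 1 − 0.966^20 and 1 − (20/22)^20. Conversion is only a proxy for non-implant. The 3.4% comes with 17.2 months' average follow-up, and the 22-patient cohort is not split by implant status. The same section reports technical success in all 15 patients of one series and deployment of all endografts in a 10-patient series. The frequency is not known from these documents.

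Downward bias is plausible but not shown. Section 2.1.1 cites 50% one-month survival without surgery, but no passage gives mortality after an aborted implant. Fatal events are also reportable to FDA within five working days (Section 3.3.4.8), monitoring checks documentation of deaths (Section 5.1), and a Termination form is completed for every subject (Section 3.3.4.10). In-hospital deaths would probably be captured; deaths after discharge in an unfollowed subject might not be.

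Finally, limiting the ITT report to 30 days would also reconcile much of the text in an early feasibility study. It would still require withdrawing the waiver for aborted cases, and would not help subjects implanted and later converted.

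**Conclusion.** The concern holds as a failure to assure the data. Sections 3.3.4.1, 3.3.4.8 and 3.3.4.9 give inconsistent follow-up, and the ITT report promised in Section 3.3.5.3 is exposed at 30 days and 1 year for aborted cases, and at 2 and 5 years for aborted, observed or converted cases. The 2- and 5-year results of the implanted set are exposed too, through subjects implanted and later converted.

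The size depends on how many subjects are affected, which is an assumption, and on an ITT set of 20. The 30-day ITT conclusion becomes undetermined with one unknown if exactly one death is known, or with two if none is known. The implanted-set 30-day test is not altered by non-implanted subjects.

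**What to change.** Replace the separate statements in Sections 3.3.4.1, 3.3.4.8 and 3.3.4.9 with one data-collection rule, and cross-refer to it from Section 3.3.5.3:

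- Delete the one-month limit in Section 3.3.4.1 and the follow-up waiver in Section 3.3.4.9. Bring the 12-month statements in Sections 3.3.4.8 and 3.3.4.9 into line with the common rule.
- For every enrolled subject, whether implanted, aborted, observed or converted, confirm vital status on or after day 30, even if the one-month visit falls earlier.
- Then follow each of them to 5 years for vital status, stroke, re-intervention and conversion, by telephone or record check where device imaging does not apply.
- Report any ITT subject of unknown status with best-case and worst-case bounds at each time point, keeping that subject in the denominator.

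The cost is protocol wording and a few extra contacts for the small number of subjects affected, with no added imaging. The rule concerns data collection only and leaves clinical care as it is.

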3.3.4.2. Implant Procedures/Treatment

All investigators will read, understand and be trained to the Medtronic Thoracic Stent Graft System Instructions for Use (IFU) (please see Appendix 14) prior to initiation of the procedure.

The principles of endovascular repair of the type A dissections is very similar to the approach to the type B aortic dissection. The route of access is either through the iliofemoral vessels, the brachiocephalic vessels, or a transapical approach via a small left thoracotomy. Through and through true-lumen access with the guidewire is confirmed using the intravascular ultrasound (IVUS) and anatomic information obtained by pre-procedural computer tomography angiogram (CTA). The size of the stent graft is selected based on the CTA and the IVUS- interrogation. The stent graft will then be delivered and deployed in the ascending aorta using a stiff guidewire. An aortic angiogram is performed to delineate the location of the coronary arteries and the innominate artery as they relate to the true and false lumen. A dissection occurs when a tear of the intima (the inner lining) allows blood to leak into the media (middle layer). This creates two passages for blood: a true lumen, which is the normal passageway of blood, and a false lumen, the newly created passageway. The cardiac cycle will be transiently halted by administration of intravenous adenosine or rapid ventricular pacing. Both methods are well established for effectively reducing the impulsive force of the cardiac output by temporarily halting the heart rate or reducing left ventricular filling, respectively. These methods allow for controlled and precise placement of the stent graft in the desired location of interest.

The usual and customary monitoring associated with procedures for the ascending aorta and arch will be utilized. These include but are not limited to multiple invasive arterial monitoring (at

least 1 radial and 1 femoral line), Cerebral oximetry, Massimo 4 channel continuous EEG monitoring, internal jugular or subclavian venous access to allow for swan-ganz catheter.

The following events will be documented in the medical records and in the CRFs as applicable:

- General, regional, or local anesthesia will be employed during the endovascular procedure per Investigator's discretion. The method of anesthesia will be documented.
- Antibiotics will be administered per Investigator's standard regimen.
- Arterial site will be accessed per Investigator's standard method.
- Systemic heparin will be administered per the Institution's standard regimen at any time during the procedure.
- Verification of dimensions and characterization of the dissection and pertinent arteries will be conducted with an angiogram at the time of the procedure and prior to the insertion of the Medtronic Thoracic Stent Graft System. The Investigator will verify dimensions and characterizations of the subject's anatomy in relation to the Medtronic Thoracic Stent Graft System. Subjects who are found not to be candidates for Medtronic Thoracic Stent Graft System, because of findings detected during the treatment angiogram, will be documented as screen failures on the Screening Log.
- All Medtronic Thoracic Stent Graft System used for implantation and any issues related to the Medtronic Thoracic Stent Graft System will be documented in the medical chart and on the CRFs.
- Fluoroscopic guidance will be used for placement of the stent graft throughout the endovascular procedure. Total fluoroscopic time and the amount of contrast media used will be documented on the operative notes.
- Devices should be deployed following all the steps in the IFU.
- At the discretion of the Investigator, Intravascular Ultrasound (IVUS) may be used in conjunction with procedural angiography to verify the position of the proximal entry tear or luminal characteristics and to optimize implantation of the device. Additional procedures performed during the treatment will be documented on the appropriate CRFs.
- Upon completion of the procedure, a final run-off angiography will be performed to document the status of the Medtronic Thoracic Stent Graft System, the coverage of the proximal entry tear and the surrounding vasculature.
- The estimated volume of blood replaced, any technical observations and adverse events experienced during the treatment will be documented.
- The cut-down site, if necessary, will be closed as per standard of care.

